# Appendix 7 B-Cell Reference Ranges by Week of Life: Absolute and Percentage Counts

TABLE III. B-cell reference ranges by week of life: Absolute and percentage counts

Week	Mean				Percentage B-cell count (%)	
1	moun	LLN*	ULN†	Mean	LLN*	ULN†
1	452	127	1165	11.3	4.6	23.1
2	513	144	1322	12.1	5.0	24.9
3	577	163	1489	13.1	5.4	26.8
4	645	182	1664	14.0	5.8	28.7
5	716	202	1846	14.9	6.1	30.5
6	788	222	2033	15.8	6.5	32.4
7	863	243	2225	16.7	6.9	34.3
8	937	264	2418	17.6	7.2	36.1
9	1012	285	2612	18.4	7.6	37.8
10	1087	306	2803	19.3	7.9	39.5
11	1159	327	2991	20.0	8.3	41.1
12	1230	346	3172	20.8	8.6	42.7
13	1297	365	3346	21.5	8.9	44.1
14	1361	383	3511	22.2	9.1	45.5
15	1420	400	3665	22.8	9.4	46.8
16	1475	416	3807	23.4	9.6	47.9
17	1525	430	3935	23.9	9.8	49.0
18	1570	442	4050	24.3	10.0	49.9
19	1609	453	4151	24.7	10.2	50.7
20	1642	463	4237	25.1	10.3	51.5
21	1670	470	4308	25.4	10.5	52.1
22	1692	477	4364	25.6	10.6	52.5
23	1708	481	4406	25.8	10.6	52.9
24	1719	484	4435	25.9	10.7	53.2
25	1725	486	4450	26.0	10.7	53.4
26	1726	486	4453	26.1	10.7	53.5
27	1723	485	4445	26.1	10.8	53.5
28	1716	483	4426	26.1	10.7	53.5
29	1705	480	4398	26.0	10.7	53.3
30	1691	476	4362	25.9	10.7	53.2
31	1675	472	4319	25.8	10.6	52.9
32	1656	466	4270	25.6	10.6	52.6
33	1635	460	4216	25.5	10.5	52.3
34	1613	454	4159	25.3	10.4	51.9
35	1589	448	4099	25.1	10.3	51.5
36	1566	441	4037	24.9	10.3	51.0
37	1541	434	3975	24.7	10.2	50.6
38	1517	427	3912	24.4	10.1	50.1
39	1494	421	3851	24.2	10.0	49.7
40	1471	414	3792	24.0	9.9	49.2
41	1449	408	3735	23.8	9.8	48.8
42	1428	402	3682	23.6	9.7	48.4
43	1409	397	3632	23.4	9.6	48.0
44	1391	392	3588	23.2	9.6	47.6
45	1376	388	3548	23.0	9.5	47.3
46 46	1363	384	3515	22.9	9.4	47.3
47	1352	381	3488	22.8	9.4	46.7
48	1345	379	3468	22.7	9.4	46.7
49	1340	377	3456	22.6	9.3	46.3
50	1339	377	3452	22.5	9.3	46.2
51	1341	378	3458	22.5	9.3	46.2
52	1347	379	3475	22.5	9.3	46.3

LLN, Lower limit of normal; ULN, Upper limit of normal. \*Defined as the 2.5th percentile of B-cell count. †Defined as the 97.5th percentile of B-cell count.

Abbreviation Definition

NK Natural Killer

PASI Pharmacokinetic Analysis Set Infants
PASM Pharmacokinetic Analysis Set Mothers

PCV-13 13-Valent Pneumococcal Conjugate Vaccine

PK Pharmacokinetic

PPMS Primary Progressive Multiple Sclerosis

PT Preferred Term
RBC Red Blood Cell

RRMS Relapsing Remitting Multiple Sclerosis

SAE Serious Adverse Event

SAFI Safety Analysis Set of Infants
SAFM Safety Analysis Set of Mothers

SAP Statistical Analysis Plan
SD Standard Deviation
SOC System Organ Class

SPMS Secondary Progressive Multiple Sclerosis
TEAE Treatment-Emergent Adverse Event

US United States
WBC White Blood Cell

WHO World Health Organization

1. BACKGROUND

Multiple sclerosis (MS) is a chronic, inflammatory, demyelinating and degenerative disease of the central nervous system (CNS) that affects approximately 1 million people in the United States (US) and 2.8 million worldwide.

Ocrelizumab is a recombinant humanized monoclonal antibody (mAb) that selectively targets and eliminates CD20-expressing B cells, which are believed to play a critical role in MS. Efficacy and safety of ocrelizumab has been demonstrated in one Phase II and three Phase III randomized controlled clinical trials.

Given the unmet need for women with MS who may wish to breastfeed but are at high risk of post-partum relapses, and given the available evidence of minimal transfer of rituximab into breastmilk, a dedicated prospective interventional study to specifically evaluate the transfer of ocrelizumab into breastmilk and the corresponding pharmacodynamic effects in infants is therefore required, and justified. This study (SOPRANINO) is part of the Sponsor's broader research effort to investigate the benefit-risk of exposure to ocrelizumab during pregnancy and lactation.

2. STUDY DESIGN

This is a prospective, multicenter, open-label study in lactating women with clinically isolated syndrome (CIS) or MS (in line with the locally approved indications) who decided together with their treating physician to continue on, or start treatment with, OCREVUS® (ocrelizumab) post-partum despite ocrelizumab currently not being recommended during lactation.

This study will enroll at least 10 women with CIS or MS who are breastfeeding or planning to breastfeed. Laboratory and clinical assessments will be performed as described in the Schedule of Assessments presented in Appendix 2.

The study will consist of the following periods:

- Screening period
- Treatment and sampling period
- Vaccination period

Figure 1 presents an overview of the study design. The schedule of assessments is provided in Appendix 2.

n=20 women/infants Treatment and sampling period Vaccination period Week Week Birth ~Month 13 Infant age 2-24 6-28 (1 month post-MMR) Day Day 14* 15* Day 30 (± 2 days) Day 60 (± 2 days) Day Day Study visit OCR infusion Co-Primary Endpoint Milk sample ocrelizumab via breastmill **Blood sample** 0 (mother & infant) Clinical visits Questionnaires & Growth Charts

Figure 1 Overview of Study Design

Samples and visits at Days 14, 15 and 21 apply only to patients initiating treatment with ocrelizumab at 2×300 mg separated by a 14-day interval.

ASQ-3=Ages and Stages Questionnaire, version 3; CIS=Clinically isolated syndrome; LMP=last menstrual period; MS=Multiple Sclerosis; OCR=Ocrelizumab.

Study description: In this prospective, multicenter, open-label study, lactating women with CIS or MS (in line with the locally approved indications) who decided together with their treating physician to continue on, or start treatment with, commercial ocrelizumab post-partum will enter a screening period, which may be started during the third trimester of pregnancy and continue until 24 weeks post-partum. Women who have delivered a healthy term infant and made a decision to breastfeed their infant will be enrolled if they and their infants fulfil the respective eligibility criteria. Women resuming treatment with ocrelizumab post-partum will be included only if the last exposure to ocrelizumab occurred more than 3 months before the LMP (i.e., women without potential fetal exposure). In the 60-day (±2 days) treatment and sampling period, women will receive the ocrelizumab dose regimen as per the locally-approved label, at any point between Week 2 and Week 24 post-partum. The first dose of ocrelizumab may be administered as two 300-mg infusions separated by 14 days (for those initiating ocrelizumab) or as a single 600-mg infusion (for those resuming ocrelizumab). For women where a decision not to administer a second 300 mg infusion is taken after enrolment, continuation in the study will be allowed. Women referred by healthcare professionals to participate in the trial may receive ocrelizumab treatment at their neurologist's site as part of their standard of care treatment. Laboratory and clinical assessments will be performed at the designated visits.

Women will collect their breastmilk samples over several time points up to $60~(\pm 2)$ days after the first post-partum ocrelizumab infusion, reserving 5 mL at each sampling point for analysis of ocrelizumab concentrations. Infant blood samples will be collected at Day $30~(\pm 2~{\rm days})$ after the first post-partum ocrelizumab infusion (regardless of whether women receive a $600~{\rm mg}$ or a $2\times300~{\rm mg}$ dose). Infant blood samples may be collected at home by a visiting nurse, if not collected at the clinical site during a study visit. In **the vaccination period,** infants will continue to be followed-up for growth and developmental milestones up to 12 months of age, using appropriate growth charts, absolute values and the ASQ-3 questionnaire (other standard measurements recorded by for example, the pediatrician as part of routine postnatal care, may also be used). Infant laboratory assessments will be performed 1 month (+ $30~{\rm days}$) after the first dose

of MMR vaccine (if first dose is administered at 11 months of age or later) or 1 month (+ 30 days) after second dose of MMR vaccine (if first dose is administered before 11 months of age), or at Month 13 of chronological age (+ 30 days) if MMR vaccine is not planned to be administered, to evaluate whether infants are able to mount humoral immune responses to clinically-relevant vaccines, and for measurement of B-cell levels. A structured telephone interview will be conducted by site personnel post-partum every 3 months (in-between ocrelizumab infusions) for a general review, and to identify and collect information on any changes in the woman's or infant's health status (including the occurrence of MS relapses in the mother and use of new concomitant medications) and possible adverse events in both the woman and the infant (particularly infections); women will also be asked if the ASQ-3 form is being filled out. No telephone contact is needed in weeks where the woman is performing on-site visits. Women who decide to discontinue the study (this includes discontinuation of either the mother or the infant) will be invited to attend an early study discontinuation visit as soon as possible (this visit may be conducted virtually or by telephone).

Further details of the procedures during each period can be found in the protocol.

2.1 PROTOCOL SYNOPSIS

The Protocol Synopsis is in Appendix 1 – please refer here for the list of objectives and corresponding endpoints. For additional details, see the Schedule of Assessments in Appendix 2.

2.2 DETERMINATION OF SAMPLE SIZE

There is no formal sample size calculation, as no confirmatory hypothesis testing is planned. The primary analysis will be descriptive. The study will include at least 10 women with CIS or MS (in line with the locally approved indications) who are breastfeeding or planning to breastfeed.

With 10 infants, a precision (width of the two-sided 95% CI) of 0.443 is expected if one event is observed (defined as B cells below the lower limit of normal [LLN]) and a precision of 0.531 if two events are observed in the study. If no event is observed during the study, there is a 95% confidence that the event rate is below 0.31.

2.3 ANALYSIS TIMING

The primary analysis will be conducted after the last breastmilk sample collection at the end of the 60-day Treatment and Sampling Period.

The full analysis, including analysis of the vaccination response in infants, will be conducted at the end of the study. The end of the study is defined as the date of the last assessment (vaccine response titers measured 1 month (+30 days) after the first or second dose of Measles Mumps and Rubella (MMR) vaccine, or at month 13 of age [+30 days] if MMR vaccine is not planned to be administered) for the last infant.

No formal effectiveness and safety interim analyses are planned. Interim analyses for administrative or scientific purposes may be conducted during the course of the study.

3. STUDY CONDUCT

3.1 RANDOMIZATION

No randomization, treatment assignment or blinding is planned.

3.2 INDEPENDENT REVIEW FACILITY

Not applicable to this study.

3.3 DATA MONITORING

There is no Independent Data Monitoring Committee (IDMC) planned for this study.

4. STATISTICAL METHODS

The analysis of this open-label study will be primarily based on descriptive statistical methods. Unless otherwise specified, statistical tests will be exploratory in nature. Corresponding 95% confidence interval (CI) will be presented as appropriate. No correction for multiple testing will be applied.

For continuous variables, descriptive statistics (e.g., number of patients [n], mean, standard deviation [SD], median, 25th and 75th percentiles, minimum, maximum) will be calculated and summarized.

For categorical variables, the number and percentage in each category will be displayed.

Unless specified otherwise, values at the mother's first ocrelizumab infusion visit (which may take place any time between Week 2 and Week 24 post-partum) will be considered as baseline for all analyses. For analyses in the infant, date of birth will be considered as baseline.

Note that the protocol's Schedule of Assessments (see Appendix 2) defines the day of first post-partum ocrelizumab administration as Day 0, whereas per the Clinical Data Interchange Standards Consortium (CDISC) standards the analysis defines it as Day 1, i.e., Study Day=Date of assessment – Day of first post-partum ocrelizumab dose + 1. Study day will be defined in the footnotes of outputs as appropriate. The primary analysis time point will be described as the "Day 30 Visit" to highlight that it refers to the visit label defined in the protocol rather than the derived study day for analysis, since in this case the derived Study Day=31.

The analyses outlined in this Statistical Analysis Plan (SAP) supersede those specified in the protocol.

4.1 ANALYSIS SETS

4.1.1 Screened Set (Mothers)

All mothers who had informed consent signed.

4.1.2 Enrolled Set (Mothers)

All mothers who were enrolled into the study.

4.1.3 Enrolled Set (Infants)

All infants who were enrolled into the study.

4.1.4 Full Analysis Set (Mothers)

The full analysis set of mothers (Full Analysis Set Mothers [FASM]) will include all enrolled mothers who receive any post-partum dose of ocrelizumab.

4.1.5 Full Analysis Set (Infants)

The full analysis set of infants (FASI) will include all the infants of women in the FASM population.

4.1.6 Full Analysis Set (Mothers & Infants)

The full analysis set (FAS) will include the combined population of infants and mothers in the FASI and FASM respectively.

4.1.7 Pharmacokinetic-Analysis Set (Mothers)

The pharmacokinetic (PK) analysis set of mothers (PASM) will include all women in the FASM with a sufficient number of ocrelizumab concentration samples from breastmilk to allow calculation of PK parameters. This analysis set will be used to estimate the PK parameters of ocrelizumab in the breastmilk of lactating women with CIS or MS receiving ocrelizumab post-partum.

4.1.8 Pharmacokinetic-Analysis Set (Infants)

The PK analysis set of infants (PASI) will include all infants in the FASI with a serum sample to allow measurement of ocrelizumab concentration. This analysis set will be used to estimate the serum concentration of ocrelizumab in the infant due to ocrelizumab transfer from the mother to the infant via breastmilk.

4.1.9 Safety Analysis Set (Mothers)

The safety analysis set of mothers (SAFM) will be the same as the FASM.

4.1.10 Safety Analysis Set (Infants)

The safety analysis set of infants (SAFI) will be the same as the FASI.

4.1.11 Antibody Immune Response Analysis Set (Infants)

The antibody immune response analysis set of infants (AIRI) will include all infants in the SAFI for whom any serum titers of antibody immune response to vaccinations are available. This analysis set will be used to analyze humoral immune responses to common childhood immunizations.

4.2 ANALYSIS OF STUDY CONDUCT

Patient disposition information will be summarized separately for the mother and infant, as: the reason and number of screen failures (mother only), the number enrolled, in the respective FAS population, in the respective safety analysis set (SAF) population, completed the treatment and sampling period, discontinued from treatment and sampling period and the reasons for discontinuation, completed the vaccination period, discontinued study and the reasons for study discontinuation.

Disposition information will be listed for mother/infant pairs in a single combined listing.

Mothers and infants who discontinued from the treatment and sampling period will be listed including reasons for discontinuation.

Time on study (weeks) will be summarized for mothers and infants, and calculated as: (date of last assessment* – date of mother's 1st post-partum ocrelizumab dose + 1) / 7.

* Date of last assessment for a subject is defined as the maximum of study completion/discontinuation date and the latest recorded date in all CRF and non-CRF data.

Major protocol deviations, including deviations of inclusion/exclusion criteria, will be summarized in the FAS of mother/infant pairs.

The number enrolled by site and country will be summarized in the enrolled population of mother/infant pairs.

4.3 Demographic and Baseline Characteristics

4.3.1 Mothers

The following demographic, MS history, baseline disease characteristics of mothers will be summarized and listed in the FASM, unless otherwise stated:

Demographic and Baseline Characteristics

- Age at screening (years) as continuous and categorical (18 to ≤30, >30 to ≤35, >35 to ≤40, >40)
- Self-reported race and ethnicity
- Height (cm), weight (kg), and Body Mass Index (BMI: kg/m²)
- Smoking history (never, current, former)
- If previous smoker, time (years) since last use

- Alcohol use history (never, current, former)
- If previous user of alcohol, time (years) since last use
- Number of weeks post-partum
- Fertility status (listing only)

Multiple Sclerosis History

- Medical condition (Relapsing Remitting Multiple Sclerosis [RRMS], Secondary Progressive Multiple Sclerosis [SPMS], Primary Progressive Multiple Sclerosis [PPMS], CIS)
- Duration (years) since onset of MS symptoms and its category (≤3 years, >3 to ≤5 years, >5 years to ≤10 years, >10 years to ≤15 years, > 15 years)
- Duration (years) since MS diagnosis and its category (≤ 3 years, >3 to
 ≤5 years, >5 years to ≤10 years, >10 years to ≤15 years, > 15 years)
- Expanded Disability Status Scale (EDSS) details up to 1 year prior to pregnancy
- Number of EDSS assessments and its category (0, 1, ≥2)
- Most recent EDSS score
- Change in EDSS score from last pre-baseline measurement (up to 1 year before LMP) to baseline

Multiple Sclerosis History - Relapse

- Number of relapses up to 1 year prior to pregnancy and its category (0, 1, 2, 3 and $\geq 4)$
- Women with relapses up to 1 year prior to pregnancy (Yes, No)
- Duration (months) since last onset of MS relapse prior to enrollment and its category (≤6 months, >6 and ≤12 months, >12 and ≤18 months, >18 months)

If the date of the relapse is completely missing or if only the year is available, the patient will be excluded from the analysis as appropriate. If the day is missing but the month is available, it will be imputed to the first day of the month.

Multiple Sclerosis History - Prior Disease Modifying Therapies Use

- Number of Disease Modifying Therapies (DMTs) used prior to pregnancy (1, 2, 3 and >3)
- Type of DMTs used prior to pregnancy
- Number of DMTs used during pregnancy (1, 2, 3 and >3)
- Type of DMTs used during pregnancy
- Number of DMTs used post-partum but before baseline (1, 2, 3 and >3)

- Type of DMTs used post-partum but before baseline
- Number of patients by the most recent DMT
- Reason for discontinuing most recent DMT
- Duration of the most recent DMT as continuous and categorical (≤6 months, >6 and ≤12 months, >12 and ≤24 months, >24 months)
- Time (months) from last DMT to LMP prior to study
- Time (months) from last DMT to first ocrelizumab prior to study

Multiple Sclerosis History - Prior Ocrelizumab Use

- Received ocrelizumab prior to the study (Yes, No)
- Duration (months) of ocrelizumab therapy prior to enrolment
- Duration of ocrelizumab therapy prior to enrolment (≤6 months, >6 and ≤12 months, >12 and ≤24 months, >24 months)
- Time (months) between last ocrelizumab infusion and the last menstrual period (LMP) (3 to ≤6 months, >6- to ≤9 months, >9 to ≤12 months, >12 months)
- Time (months) between delivery and first post-partum ocrelizumab infusion

Baseline Disease Characteristics

- Baseline EDSS continuous
- Baseline EDSS distribution: count and percent of patients corresponding to each observed score of EDSS at baseline
- For those who underwent neurological examination at baseline, any new clinically significant abnormalities since last exam (Yes, No)
- Type of abnormality for those with clinically significant abnormalities since last exam (disability progression independent of relapse, MS relapse, signs or symptoms suggestive of Progressive Multifocal Leukoencephalopathy, Other)

Obstetric and Gynecological History

- History of previous pregnancies (Yes/No)
- Number of previous pregnancies (1, 2, 3, 4, >4)
- Previous pregnancy outcome (Full term live birth, preterm live birth, spontaneous abortion, still birth, therapeutic abortion, elective abortion, ectopic pregnancy, unknown)
- History of obstetrical complications during previous pregnancies (Yes/No)

Medical History

Medical history of the mother will be summarized in the SAFM by SOC and PT. For each previous and concurrent medical history recorded medical history (MH), the term entered

by the investigator describing the event (the "reported term") will be assigned a standardized term (the "Preferred Term" [PT]) and assigned to a superclass term (the "System Organ Class" [SOC]) on the basis of the MedDRA World Health Organization (WHO) dictionary of terms.

Vaccination History

Severe acute respiratory syndrome coronavirus 2 (SARS-CoV-2) vaccination and non-SARS-CoV-2 vaccination history will be summarised in the SAFM overall and split by the period prior to infant's birth and before/after LMP and after infant's birth. Where time period cannot be determined due to completely or partially missing date, it will be imputed to before infant's birth.

SARS-CoV-2 vaccination history will also be listed in the SAFM, including the following:

- Manufacturer name (first, second and, if applicable third dose and any booster dose(s)) (Pfizer/BioNTech Covid-19 vaccine, Moderna Covid-19 vaccine, Astra Zeneca Covid-19 vaccine, Johnson & Johnson Covid-19 vaccine, Other)
- Type of vaccine for each dose (mRNA vaccine, Viral Vector Vaccine, Inactivated Vaccine, Other)
- Timepoint of last COVID-19 vaccination prior to enrollment (>6 months before pregnancy, ≤6 months before pregnancy, 1st trimester, 2nd trimester, 3rd trimester, ≤6 months post-partum, >6 months post-partum)

Other vaccination history (vaccines other than SARS-CoV-2) will also be listed in the SAFM.

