To measure disease activity in lactating women with CIS or MS receiving ocrelizumab postpartum	
 
Number of MS relapses during the postpartum period (clinical relapses)
 
Mean change in the EDSS score from last pre-baseline measurement (up to 1 year before LMP) to baseline
 

To evaluate the evolution of B-cell levels over the first year of life in infants of lactating women with CIS or MS receiving ocrelizumab postpartum	Trajectory (absolute and percentage changes) of B-cells (CD19+ cells) in the infant from Day 30 after the mother's first ocrelizumab postpartum infusion to 1 month after the first or second dose of MMR vaccine, or Month 13 of age in case MMR vaccine is not planned to be administered

ADID=average oral daily infant dosage; ASQ-3=Ages and Stages Questionnaire version 3; AUC=area under the milk concentration-time curve; CIS=clinically isolated syndrome; EDSS=Expanded Disability Status Scale; HBV=hepatitis B virus; Hib=Hemophilus influenzae type b; LLN=lower limit of normal; LMP=last menstrual period; MDID=maximum oral daily infant dosage; MMR=measles, mumps, and rubella MS=multiple sclerosis; PCV-13=13-pneumococcal conjugate vaccine; RID = relative infant dose; WHO=World Health Organization.

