### 4.5.2.6 Assessment of Disability

Disability in MS will be measured by the EDSS. See Appendix 1 (Schedule of Assessments) for the timing of assessments.

The EDSS is based on a standard neurological examination, incorporating seven functional systems (pyramidal, cerebellar, brainstem, sensory, bowel and bladder, visual, and cerebral [or mental], plus "other") rated and scored as FSSs. Each FSS is an ordinal clinical rating scale ranging from 0 to 5 or 6. These ratings are then used in conjunction with observations and information concerning ambulation and use of assistive devices to determine the EDSS score. The EDSS is a disability scale that ranges in 0.5-point steps from 0 (normal) to 10 (death) (see Appendix 4). The EDSS assessment may also be performed by the investigator via telephone, using a specific licensed questionnaire (see Appendix A4–2).

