# A4–1 EDSS STEPS

0	Normal neurological exam (all FS Grade 0)
1.0	No disability, minimal signs in one FS (one FS Grade 1)
1.5	No disability, minimal signs in more than one FS (more than one FS Grade 1)
2.0	Minimal disability in one FS (one FS Grade 2, others 0 or 1)
2.5	Minimal disability in two FS (two FS Grade 2, others 0 or 1)
3.0	Fully ambulatory but with moderate disability in one FS (one FS Grade 3, others 0 or 1) OR Fully ambulatory but with mild disability in three or four FS (three/four FS Grade 2, others 0 or 1)
3.5	Fully ambulatory but with moderate disability in one FS (one FS Grade 3) and mild disability in one or two FS (one/two FS Grade 2) and others 0 or 1; OR Fully ambulatory with two FS Grade 3 (others 0 or 1); OR Fully ambulatory with five FS Grade 2 (others 0 or 1)
4.0	Fully ambulatory for ≥500 meters without aid or rest; up and about some 12 hours a day characterized by relatively severe disability consisting of one FS Grade 4 (others 0 or 1) or combinations of lesser grades exceeding limits of previous steps
4.5	Ambulatory for 300–500 meters without aid or rest; up and about much of the day, characterized by relatively severe disability usually consisting of one FS Grade 4 and combination of lesser grades exceeding limits of previous steps
5.0	Ambulatory for 200–300 meters without aid or rest (usual FS equivalents include at
	least one FS Grade 5, or combinations of lesser grades usually exceeding specifications for step 4.5)
5.5	
5.5	for step 4.5)
	for step 4.5)  Ambulatory for 100–200 meters without aid or rest  Ambulatory for at least 100 meters with intermittent or constant unilateral assistance (cane or crutch) with or without rest OR  Ambulatory < 100 meters without help or assistance OR  Ambulatory ≥ 50 meters with unilateral assistance OR
6.0	for step 4.5)  Ambulatory for 100–200 meters without aid or rest  Ambulatory for at least 100 meters with intermittent or constant unilateral assistance (cane or crutch) with or without rest OR  Ambulatory < 100 meters without help or assistance OR  Ambulatory ≥ 50 meters with unilateral assistance OR  Ambulatory ≥ 120 meters with bilateral assistance  Ambulatory for at least 20 meters with constant bilateral assistance (canes or crutches) without rest OR  Ambulatory for < 50 meters with unilateral assistance (cane or crutch) OR

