# A4-2 EDSS BY TELEPHONE

#### **EDSS BY PHONE**

The purpose of this interview is to obtain the best possible estimate of the Expanded Disability Status Scale (EDSS) score of patients who exceptionally cannot come to the study centre and be examined by a neurologist. The current version is using the Neurostatus definitions version 04/10.2 but is fully compatible with previous versions. Ideally the same EDSS physician who assessed the patient at the last visit should do the standardized interview for EDSS by phone. The interview should be done with the patient himself. If the patient cannot be interviewed due his health condition, the interview may be done with a caregiver or his or her physician.

Question the patient about the current status (or a specified time period in the past) until the EDSS score becomes clear. Some questions may have to be modified according to the patient's last disability status since the answer may be known before asking, e.g. if the patient is wheel-chair bound, the question "do you have any disability" may be superfluous and may sound offending to some patients. Generally, the questions exploring disability scores lower than the last known EDSS score may be superfluous.

The functional system (FS) and EDSS scores should reflect MS related deficits only. In case of doubt the examining physician should assume a relation to MS. Temporary signs or symptoms that are not due to multiple sclerosis, e.g. temporal immobilisation after fracture of one limb, as well as permanent signs or symptoms that are not due to multiple sclerosis, e.g. leg amputation after accident, will not be taken into consideration when assessing the FS scores and EDSS steps, but need to be noted in the questionnaire. A "P" next to the respective entry indicates permanent non MS related deficits, a "T" temporary non MS related deficits.

© 2013 [name] and [name], MD, Neurology, University Hospitals Basel, 4031 Basel, Switzerland; slightly modified to original Version 2003

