#### Sensory FS

When touching your body, is the sensation normal?

- 0 = yes
- 2 = no, numbness when touching of 1 or 2 limbs
- 3 = no, clearly decreased sensation in 1 or 2 limbs or numbness in many parts of the body below the head
- 4 = no, even forced touching is not felt at all in 1 or 2 limbs or just clearly decreased sensation in more than 2 limbs
- 5 = no, sensation essentially lost in 1 or 2 limbs or moderate decrease of sensation for most of the body below the head
- 6 = no, sensation essentially lost below the head

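### EDSS change to baseline ignores mode of assessment, although the printed telephone options offer grade 1 for vision only and cannot return EDSS 1.5

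*SAP*

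**What the plan says.** Protocol Section 2 lists as an exploratory endpoint "Mean change in the EDSS score from last pre-baseline measurement (up to 1 year before LMP) to baseline". SAP 4.3.1 carries it under multiple sclerosis history as "Change in EDSS score from last pre-baseline measurement (up to 1 year before LMP) to baseline". Among baseline disease characteristics it adds "Baseline EDSS distribution: count and percent of patients corresponding to each observed score of EDSS at baseline". SAP 4.6.3 adds EDSS listings. None of these places names the mode of assessment, and no flag, subgroup or sensitivity analysis by mode is planned.

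Protocol 4.5.2.6 states: "The EDSS assessment may also be performed by the investigator via telephone, using a specific licensed questionnaire". The form is in Appendix A4-2, whose stated purpose is to "obtain the best possible estimate of the Expanded Disability Status Scale (EDSS) score of patients who exceptionally cannot come to the study centre". The EDSS steps in A4-1 need grade 1 scores for the two lowest non-zero values: 1.0 is one FS at grade 1, and 1.5 is "No disability, minimal signs in more than one FS (more than one FS Grade 1").

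**The concern.** The two instruments do not share the same grid at the low end. A change score subtracts one from the other whenever a woman was examined before pregnancy and telephoned at baseline. If her only findings are grade 1 signs, the telephone form must usually round them down to 0 or up to 2, so the difference is non-zero even when her disability has not changed.

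Such pairs are plausible in this trial. Protocol 3.1 allows referral from other centers and home-based visits with the investigator working remotely. Protocol 3.1.3 allows referred women to be infused at their own neurologist's site. Protocol 4.5.2.1 collects the earlier EDSS as history, where available. With about 10 women, a single pair is visible in the mean. The baseline distribution would also contain no telephone score of 1.5, for a reason that has nothing to do with the women.

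**Working it through.** The plan gives no sample size, precision or expected value for the EDSS change, so there is no figure to reproduce.

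**Inputs**
- Telephone options (Protocol A4-2, item 8). Visual offers 0, 1, 2, 3, 4. Brainstem, pyramidal, cerebellar, sensory, bowel and bladder, and cerebral go from 0 to 2 or higher. The sensory item, for example, goes from a normal answer straight to "2 = no, numbness when touching of 1 or 2 limbs". Protocol versions 3 and 4 print the same options.
- Examination grades (Protocol Appendix 4, Functional System Scores): grade 1 exists in all seven systems.
- EDSS steps (A4-1): all FS 0 gives 0; one FS at 1 gives 1.0; two or more at 1 gives 1.5; one FS at 2 with the others 0 or 1 gives 2.0; two at 2 gives 2.5; three or four at 2 gives 3.0.
- Scoring rule (A4-2, item 8): when walking distance is at least 500 m, the FS combination alone sets the EDSS.
- Planned minimum of 10 women (SAP 2).

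**Step 1: which low scores are reachable.** With seven systems each graded 0 or 1 there are 2^7 = 128 patterns. By examination, 1 gives EDSS 0, 7 give 1.0 and 128 - 1 - 7 = 120 give 1.5. On the printed telephone options only two of these patterns can be recorded: all zero (EDSS 0), and visual 1 with all others 0 (EDSS 1.0). No combination of printed options gives 1.5.

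**Step 2: how many 1.5 patterns involve vision.** Of the 128 patterns, 2^6 = 64 have visual grade 1. Removing the one with vision alone leaves 63. So 63 of the 120 patterns at 1.5 include vision, and 120 - 63 = 57 do not. These are counts of patterns, not frequencies of women.

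**Step 3: change in a stable woman.** Each non-visual grade 1 is taken to move to 0 or 2, and a visual grade 1 to stay at 1.

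| Signs at examination | Examined EDSS | Telephone EDSS | Apparent change |
|---|---|---|---|
| Visual only | 1.0 | 1.0 | 0 |
| One non-visual system | 1.0 | 0 or 2.0 | -1.0 or +1.0 |
| Two non-visual systems | 1.5 | 0, 2.0 or 2.5 | -1.5, +0.5 or +1.0 |
| Visual plus one non-visual | 1.5 | 1.0 or 2.0 | -0.5 or +0.5 |

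**Step 4: effect on the mean.** One woman with apparent change d shifts the mean of n women by d/n. With n = 10 and two non-visual systems, the shift is -1.5/10 = -0.15, +0.5/10 = +0.05 or +1.0/10 = +0.10. More grade 1 systems widen the upper end: three rounded up give 3.0, a change of +1.5 and a shift of +0.15. Shifts add across women, and opposite signs can cancel.

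**The case against.** The strongest reply is that this will rarely happen and matters little.

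- The form is meant for "patients who exceptionally cannot come to the study centre and be examined by a neurologist". Baseline is the infusion day, and the Schedule of Assessments places a neurological examination there alongside EDSS. Protocol 4.5.2.4 allows results from routine neurological examinations to be used. This stands: the documents give no count of telephone scores.
- The form sends the assessor to the full definition manual. It prefers the physician who made the last assessment and asks about change since the last visit. A known stable woman need not be scored as 0. This also stands, so the claim that 1.5 cannot be returned holds for the printed options only. It is limited by the grade 1 definitions for the brainstem, pyramidal and cerebellar systems, which rest on signs without disability; an interview cannot examine for these.
- From 2.0 up to 4.0 the A4-1 steps commonly allow the other systems at 0 or 1, so the missing grade 1 does not remove those scores.
- The endpoint is exploratory and descriptive, and it ends at baseline. It does not measure the effect of postpartum ocrelizumab and touches neither co-primary endpoint.

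What survives is that the SAP neither shows mode nor separates mixed-mode pairs, so a reader could not tell an instrument effect from a real change.

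**Conclusion.** The point holds as a minor one. On the printed options the telephone form cannot yield EDSS 1.5 and yields 1.0 only through vision, while the SAP analyzes EDSS without regard to mode. One stable woman with two non-visual grade 1 systems, examined earlier and telephoned at baseline, moves the mean of 10 women by -0.15 to +0.10. This assumes that the assessor keeps to the printed options and that the two scores were obtained by different modes.

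A reader might infer more, but the documents do not support it:
- That every examined 1.5 becomes 0 or at least 2.0. It can become 1.0 when one of the systems is vision and the others score 0.
- That 2 recordable patterns out of 128 means nearly all low scores will be wrong. The patterns are not equally likely, and the cohort's EDSS distribution is not given.
- That the mean change will be biased in a known direction or by a bounded amount. The apparent change can have either sign, and the number of affected women is unknown.
- That the SAP declares the two scales equivalent. It simply makes no distinction.

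**What to change.** In SAP 4.3.1 and 4.6.3:
- Show mode of assessment (examination, telephone, unknown) in the EDSS listing and in the baseline EDSS table.
- Keep the overall summary of change. Add a second summary limited to women with both scores by examination, and list mixed-mode and unknown-mode pairs.
- Footnote the baseline distribution to say that the printed telephone options cannot yield 1.5.

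The cost is SAP wording, one variable and one extra summary, with no new visits. Neither document says that the eCRF records mode. It would have to be confirmed from source where it is not held, and for historical scores it may stay unknown. The examination-only summary will rest on fewer women, which is why the overall summary should stay.
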